Study Title: *“Manikin To Patient Intubation: Does It Translate?”*

Principal Investigator: R. [name].
University of Arkansas for Medical Sciences
[name]
[name]
[contact]
Email: [contact]

Study Location: University of Arkansas for Medical Sciences
[name]
[name]

Date: September 19, 2017

NCT number: NCT03046966

Statistical Analysis

Chi-square tests with the Benjamani-Holm p-value correction to account for test multiplicity will be used to analyze the difference in baseline measures and demographics. Chi-square testing will be utilized for comparing end of survey comfort. Logistic regression will be utilized to compare overall and first-time intubation success rates between the control and intervention groups. Logistic regression will be used to compare the difference in success rate between training level groups. To account for over-dispersion, a negative binomial regression will be utilized to assess difference in overall and first-time intubation success counts.

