## **Abstract**

Tracheal intubation of infants and children is a critical lifesaving skill, and its importance is recognized by the Accreditation Council on Graduate Medical Education (ACGME), Residency Review Committee (RRC), the Neonatal Resuscitation Program (NRP) and Pediatric Advanced Life Support (PALS) programs. Despite its importance, current training is lacking in teaching this critical procedural skill as demonstrated by the inability of up to 1/3 of upper level Pediatric residents to be able to successfully intubate Very Low Birth Weight (VLBW, <1500 grams) neonates. New technology, which has now been adapted to the existing telemedicine network in Arkansas, offers an exciting opportunity to improve the ability of pediatric trainees to accomplish this critical task. We will utilize a deliberate practice approach with immediate feedback during neonatology rotations using the Storz video laryngoscope to teach this critical skill to Pediatric and Med-Peds residents (n=95 residents total). Previous work demonstrated improvement in skills with a manikin, but it is unknown if these skills will translate to live intubations. The residents will receive training during alternating months, and will be recorded during live intubations. We will assess how intubation skills using a manikin translates to live patients. We anticipate this training will dramatically improve intubation skills and resident confidence as evidenced by intubation accuracy.

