### **Hypothesis and/or Specific Aims or Objectives**

Specific Aim 1. *Assess the impact of this educational manikin intervention on live patients.*

We hypothesize learners in the Intervention Group vs. the Control Group will have enhanced success in intubation as determined by the number of attempts and time required for intubation of live patients.

Specific Aim 2. *Assess the satisfaction of this educational intervention and equipment.*

We hypothesize pediatric residents will have increased satisfaction scores and confidence for intubating live patients in the Intervention Group vs. the Control Group.

Specific Aim 3. *Assess the association of confidence in intubation with actual success in intubation.*

We hypothesize increased confidence will be associated with increased intubation success.

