During the monthly rotation of each resident, ongoing data will be collected on the residents' ability to successfully intubate on the first attempt, the total number of attempts to intubate, and the total number of successful attempts at intubating a neonate within 30 seconds, the time limit set by NRP. All live intubations performed in the Stabilization Rooms will be recorded and reviewed by designated members of the NICU Safety Committee. The recorded videos of study participants will also be reviewed by [name] and [name], R.N. The information obtained from the video recordings will be kept in a safe, secure file that is password protected. At the end of the monthly rotation each resident, including those in the Control Group, will be offered the opportunity to complete the Hands-on Intubation training simulation with [name].

Angel Eye Cameras and control modules will be placed on the patient beds in the NICU Resuscitation Rooms which will be used for recording and monitoring infant intubation procedures. The cameras will be placed on the bed above the infant and staff while the control panel will be on a nearby wall to allow for easy starting and stopping of recording and monitoring of recording during the procedure. The control panel will have access to start/stop

[figure not shown]

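### The SAP's only multiplicity correction covers baseline tests, while the outcome tests have no named primary and no error-control rule

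*SAP*

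**What the plan says.** The SAP's statistical section is one paragraph. Its only multiplicity rule is attached to chi-square tests at baseline: "Benjamani-Holm p-value correction to account for test multiplicity will be used to analyze the difference in baseline measures and demographics".

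The other analyses follow with no correction:
- Comfort: "Chi-square testing will be utilized for comparing end of survey comfort".
- Success rates by arm: "Logistic regression will be utilized to compare overall and first-time intubation success rates between the control and intervention groups".
- Success by training level, which does not test the intervention: "Logistic regression will be used to compare the difference in success rate between training level groups".
- Success counts, with no groups named: "To account for over-dispersion, a negative binomial regression will be utilized to assess difference in overall and first-time intubation success counts".

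Neither document states an alpha or names a primary outcome, and the places where one might be found disagree:
- The protocol Abstract expects gains "We anticipate this training will dramatically improve intubation skills and resident confidence as evidenced by intubation accuracy", which defines no endpoint.
- Aim 1 (Hypothesis and/or Specific Aims or Objectives) expects "enhanced success in intubation as determined by the number of attempts and time required for intubation of live patients".
- Methods lists three measures without ranking them: "ability to successfully intubate on the first attempt, the total number of attempts to intubate, and the total number of successful attempts", the last counted within the 30-second NRP limit.
- The Evaluation Plan gives 27 residents per group but does not say for which outcome.

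**The concern.** The authors recognised multiplicity but placed the correction where no claim about the training depends on it. The name makes matters worse. It could mean Benjamini-Hochberg, which controls the false discovery rate, or Holm, which controls the family-wise error rate.

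With several uncorrected outcome tests and no primary, a significant result on any one of them could be presented as showing that manikin training carries over to patients. The chance that such a claim is false is then well above the conventional 5%.

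A second gap adds to the first. The SAP allows for over-dispersion in the count models but states no parallel allowance in the logistic models, although one resident may intubate several infants. If the logistic unit is the intubation, each test can exceed its own 5% before multiplicity is counted.

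**Working it through.** **Figures in the plan.** The documents give no error rate to reproduce. The 27 per group cannot be reproduced either, because no endpoint, effect, alpha or power is stated. Solving backwards for two means (two-sided 5%, 80% power, both assumed) gives d = (1.960 + 0.842) × √(2/27) = 0.76.

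**Inputs.** From the documents: 27 residents per group (Evaluation Plan), or about 40 if the anticipated 80 (Methods) split equally. Assumed: 5% two-sided per test; a Poisson mean of 2 or 4 patients per resident; first-attempt success 40%; half of the remainder intubated later, so overall success is 0.40 + 0.60 × 0.50 = 0.70; one five-level comfort item; and a normal resident effect with SD 0, 0.5 or 1.0 on the logit scale. These SDs correspond to latent intraclass correlations, SD²/(SD² + π²/3), of 0, 0.07 and 0.23.

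**Step 1: upper bound.** For k independent tests, the chance of at least one false positive is 1 − 0.95^k: 9.75% for 2, 14.3% for 3 and 22.6% for 5. The success tests overlap, so the true figures are lower.

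**Step 2: check with overlap.** A first-attempt success is also an overall success. The correlation is therefore (0.40 − 0.40 × 0.70)/√(0.40 × 0.60 × 0.70 × 0.30) = 0.12/0.2245 = 0.53. For two bivariate normal statistics with that correlation, P(|Z₁| > 1.96 or |Z₂| > 1.96) = 9.0%. Adding an independent comfort test gives 1 − (1 − 0.090) × 0.95 = 13.5%.

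**Step 3: simulation of the plan as written.** Global null, 6,000 runs per setting, logistic models treating each intubation as independent. Ranges run over the arm sizes and patient numbers above.

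| Tests counted | Resident SD 0 | SD 0.5 | SD 1.0 |
|---|---|---|---|
| Two success rates | 8.8-9.7% | 11.5-14.3% | 15.9-22.0% |
| Plus one comfort item | 13.2-14.1% | 15.4-18.3% | 20.1-25.5% |
| Plus two counts, if they compare arms | 17.1-18.5% | 19.6-21.9% | 23.3-27.7% |

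The SD 0 column agrees with Step 2.

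**Step 4: both gaps matter.** With GEE success models (Mancl-DeRouen correction, t reference) but no multiplicity rule, the chance over five tests is still 15.6-17.6%. Conversely, one primary (first-attempt success as an example) tested at 5% by a model that ignores the resident rejects 4.9-5.5% of the time at SD 0, 6.0-8.4% at SD 0.5 and 9.3-13.5% at SD 1.0.

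**Step 5: the remedy without a month effect.** With the GEE models, the chance of any false positive is 3.6-4.7% for a gated primary followed by Holm, 2.7-3.9% for Holm over all five, and 6.1-7.5% for the primary at 5% with ungated Holm over the other four.

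**Step 6: the remedy with a month effect.** Allocation follows the NICU month (Abstract, Methods). With an assumed 12 alternating months, one resident-robust test rejected 3.5-5.3% of the time with no month effect, 4.8-9.4% at a month SD of 0.3 and 6.0-16.5% at 0.5. A separate simulation with resident and month SDs of 0.5 each gave 6.5-14%. The Step 5 figures therefore do not carry over unless month is handled.

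**The case against.** The best case against runs as follows. This is a small education study, and correcting secondary outcomes is a choice rather than a duty. Rates and counts analyse the same two outcomes, and only the two rate tests are explicitly between-arm comparisons of live intubation. The resident SD and the number of intubations per resident are assumptions. The SAP does not say whether the logistic unit is the resident or the intubation.

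Much of this stands. If one primary were named and the rest labelled exploratory, no further correction would be needed; what the documents lack is that designation. The two-test figure of 9-10%, with independent intubations, is the one that needs least beyond the text. The clustered figures apply only if the unit is the intubation.

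Three stronger readings are tempting but unsupported:
- That the plan has an error rate of 17-28%. This requires the counts to compare arms, and its upper part also requires an assumed SD of 1.0.
- That resident-robust models with a gate or Holm secure 5%. Step 6 shows that they need not when allocation is by month.
- That the baseline tests do harm. They leave the outcome inference untouched, and with allocation by month and residents approached after the rotation starts, looking for imbalance has some rationale.

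**Conclusion.** The concern holds in limited form and should be fixed. The documents establish that the sole correction covers only baseline tests, that its name is ambiguous, that the outcome tests have none, and that no primary outcome can be inferred.

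The size rests on assumptions: roughly double the nominal 5% for the two rate tests if intubations are independent, and up to 22% under the strongest resident correlation examined. Every setting in Step 3 exceeds 5%. Confidence is medium, because alpha, the number of intubations, the comfort scale and both correlations are not given. Adding a training-level covariate, using a rank test for comfort and removing the baseline tests are optional and not part of this conclusion.

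**What to change.** 1. Name one live-intubation primary outcome that matches Aim 1, and state its test at a two-sided 5% level. The choice is the investigators'. Aim 1 speaks of attempts and time, and the SAP currently names an analysis for neither, so the two documents need aligning.
2. Label all other outcomes secondary or exploratory. If claims will be made from them, apply a Holm correction, correctly named, with or without a gate on the primary. State whether the count models compare arms.
3. State the unit of analysis. If it is the intubation, fit the success models with allowance for repeated intubations by a resident, for example GEE with a small-sample correction.
4. Allow for correlation within NICU month before claiming 5% control.

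**Cost.** These are changes to SAP text, with no new data. Naming a primary costs it no power. Splitting alpha over the four success tests instead would set the threshold at 0.05/4 = 0.0125 and, at d = 0.76, cut power from 80% to about 62% with 27 per arm (about 82% with 40). Secondary outcomes face stricter thresholds, and intervals will be somewhat wider.

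A gate also makes Aim 2 depend on Aim 1. Suppose first-attempt success rises from 40% to 60% and comfort by 0.6 SD (both assumed), with a rank test for comfort. Power for comfort then falls from 53-70% uncorrected to 10-50% gated. Without a gate, comfort can be claimed even if the primary misses, but the chance of some false claim is 6.1-7.5% even with no month effect (Step 5).

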## **Methods**

This research study will include 95 resident physicians. We anticipate 80 residents will enroll, similar to our previous study in which 82 residents participated. Residents will be randomized to the Intervention Group or the Control Group. This study will be explained to potential participants as they begin their assigned rotation to the Neonatal Intensive Care Unit (NICU). The explanation of the study and the Information Sheet will be introduced during the first five (5) days of this rotation. Residents will be allowed to ask any questions they feel necessary and take as much time as needed in order to make a fully informed voluntary consent. It will be explained that their participation in this study is completely voluntary and a decision to not participate will have no impact on their training or standing in the residency program. Randomization will occur by the month the resident is assigned to the NICU.

All participants will:

- Receive NRP training and certification offered at the beginning of their residency
- Complete a Baseline Survey
- Complete a Baseline Cognitive and Simulation Assessment
- Have a Stabilization Room video recording as part of the quality improvement process for neonatal resuscitation
- Complete a Cognitive and Simulation Assessment at the end of the month
- Complete an End of Rotation Survey

Residents who are randomized to the Intervention Group will, in addition:

- Observe a 7 minute NRP video
- Complete a hands-on intubation simulation with [name] instructing:
  - Using state of the art technology, a Storz C-MAC video laryngoscope
  - Identifying anatomical landmarks
  - Practice on the manikin until intubation occurs within 15 seconds

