## **Evaluation Plan**

Using data from our previous intubation study using a manikin, we estimate a sample size for this study is 27 residents in each group. We recruited more than that for the manikin study, and for that study residents were required to come back for a post test. Thus, we anticipate no major difficulties in recruitment.

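### Arms are allocated by NICU month and residents may contribute several live attempts, but the SAP's logistic comparison of success states no unit of analysis and names no resident or month term

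*SAP*

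**What the plan says.** **Allocation.** The Protocol's Methods section states: "Randomization will occur by the month the resident is assigned to the NICU". The Abstract adds: "The residents will receive training during alternating months, and will be recorded during live intubations". On either wording, residents enrolled in the same month share an arm.

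**Outcome data.** Methods lists, for each resident over the rotation, the "ability to successfully intubate on the first attempt, the total number of attempts to intubate, and the total number of successful attempts" within the 30-second limit. It also says that "All live intubations performed in the Stabilization Rooms will be recorded". No cap per resident is given, so a resident may contribute more than one attempt.

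**Analysis.** The SAP is one paragraph. For the arms it says: "Logistic regression will be utilized to compare overall and first-time intubation success rates between the control and intervention groups". It names no unit of analysis, random effect, GEE, robust variance or month term. A second logistic regression compares training levels, with the same silence. A negative binomial regression, chosen for over-dispersion, is planned for overall and first-time success counts.

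**Size.** The Evaluation Plan says "we estimate a sample size for this study is 27 residents in each group", on the basis of the earlier manikin study. Methods says "We anticipate 80 residents will enroll". Neither statement mentions months as clusters.

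**The concern.** There are two possible sources of correlation. Attempts by one resident share that resident's skill. Residents in one month share an arm and may share supervision, case mix and season. Ordinary logistic regression on attempts ignores both.

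The missing unit matters because different readings give different standard errors. If first-time success is one outcome per resident, only month clustering remains. If it is one per neonate, both sources apply. Overall success invites attempt-level rows, where both apply.

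At stake is one of only two arm comparisons of live performance in the SAP. Too small a standard error produces too many false differences, in either direction, and intervals that are too narrow. If the choice is left open until the data are seen, the results can influence it.

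**Working it through.** **1. The plan's own figure.** The 27 per group cannot be reproduced, because no alpha, power, effect size, SD or success rate is given. Solving backwards with two-sided alpha 0.05 and 80% power (both assumed):

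- Means: n = 2(1.96 + 0.84)²/d² = 27 gives a standardized difference d of about 0.76 to 0.78.
- Proportions: about 50% versus 85%, without continuity correction.

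Neither solution involves clustering, and neither shows which outcome was used.

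**2. Formula check.** Design effect DE = 1 + (m − 1) × ICC. True type I error of a nominal two-sided 5% test = 2[1 − Φ(1.96/√DE)]. All ICCs and cluster sizes here are assumptions.

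| Source of clustering | m | ICC | DE | Type I error |
|---|---|---|---|---|
| Resident | 2 attempts | 0.05 | 1.05 | 5.6% |
| Resident | 3 attempts | 0.2 | 1.40 | 9.8% |
| Month, one outcome per resident | 5 residents | 0.05 | 1.20 | 7.4% |

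**3. Simulation.** Assumptions: 14 alternating months of 6 residents (84, close to the 80 expected), 50% success in both arms, resident logit SD 0.9, and either one outcome per resident or a Poisson number of attempts with mean 1.5. The test is a Wald test of the arm log odds ratio on pooled rows, with 10,000 null trials per cell.

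| Month logit SD | One outcome per resident | Mean 1.5 attempts |
|---|---|---|
| 0 | 4.7% | 7.7% |
| 0.3 | 5.7% | 8.7% |
| 0.5 | 7.5% | 11.7% |

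Repeat runs with other seeds agreed within one percentage point. Low attempt numbers are shown because the Protocol's Background describes infrequent trainee exposure to airway management, and because only Stabilization Room intubations are recorded.

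**4. Effect on a p-value.** The simulated DE in the cell with 1.5 attempts and no month effect is 1.23. The formula in step 2 gives 2[1 − Φ(1.96/√1.23)] = 7.7%, which agrees with the table. Dividing a naive z by √1.23 turns p = 0.03 into 0.050 and p = 0.001 into 0.003. Borderline results are at risk; a strong one would survive.

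**5. Alternatives.** Under the null, over layouts of 14 × 6 and 20 × 4 and the full grid of SDs and attempt numbers tried, two methods held their level:

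- Month-level t-test: 4.6% to 5.7%.
- GEE clustered on month, with a Kauermann-Carroll correction and t on months minus 2 degrees of freedom: 4.0% to 5.4%.

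Clustering on resident alone is valid when months do not differ (4.4% in the step 3 cell with 1.5 attempts). It gives 8.1% in that cell at month SD 0.5.

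**The case against.** **Silence is not a choice.** The SAP never says attempts are independent, and GEE and mixed logistic models are still logistic regression. This stands. A reader might infer that the plan commits to an analysis ignoring clustering; the documents show only that it does not specify one. The request is therefore to specify the model.

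**The negative binomial model covers it.** Fitted to one count per resident, it may absorb between-resident variation for the same two outcomes. That stands in part. It names no month term, and it does not change the logistic p-values.

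**The size is assumed throughout.** This stands. With one outcome per resident and no month effect there is no inflation. A reader might infer serious inflation from scenarios with many attempts per resident: at a mean of 5 attempts and the largest SDs tried, the simulated error is 27%. Nothing in the documents supports that many attempts, and the Background and the recording restriction point the other way.

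**The sample size.** A reader might infer that 27 per group is too small. The documents do not show this. At 5 residents per month and ICC 0.05, month clustering alone would raise it to 27 × 1.20 = 32.4, so 33. The expected 80 residents give about 40 per group.

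**Random or alternating months.** Whether months are randomized or simply alternate is a separate question about allocation. The clustering is the same either way.

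**Conclusion.** The concern holds as under-specification with a concrete consequence. Allocation is by month, repeated attempts per resident are possible, and the logistic comparison states neither its unit nor any handling of resident or month. Run on attempts as though independent, it understates the standard error whenever there is correlation within resident or month.

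Under the assumptions in steps 3 and 4 of the working, the inflation is nil to slight with one outcome per resident unless months differ appreciably, and moderate at 1.5 attempts (about 7% to 12% against a nominal 5%). None of these inputs is in the documents.

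The point should be fixed, but no stronger rating is justified. A reader might infer that the trial's main conclusion depends on this test. However, no primary endpoint is named, and Aim 1 defines success differently: "enhanced success in intubation as determined by the number of attempts and time required for intubation of live patients".

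**What to change.** **Change to the SAP:**

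- State the unit of analysis for overall success and for first-time success.
- Specify the arm comparison as a logistic GEE or mixed model that accounts for month of allocation and for repeated attempts by a resident, with a small-sample correction for few months. A month-level summary analysis is an acceptable alternative. The team may choose, but before the data are analysed.
- Say whether a resident can rotate in more than one month. The documents do not. If so, residents must not be treated as nested in months.
- Account for repeated attempts by resident in the training-level comparison.
- Keep resident code and rotation month in the analysis file.

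**Cost.** A few sentences, slightly more analysis work and no new data. Intervals widen and some power is really lost. In one assumed cell (14 × 6, 1.5 attempts, resident SD 0.9, no month effect, true log odds ratio 1.0), power is about:

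- 63% for the plain model, at a true error rate near 7.7%;
- 56% for the plain model held to a true 5%;
- 55% clustered on resident only;
- 48% for the month-level t-test, and 42% to 48% for month-clustered GEE, depending on the correction.

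Of the 15 points between 63% and 48%, about 7 come from removing the inflated error. About 8 are the price of protection against month effects, which cannot be ruled out from the documents.

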## **Project Narrative**

### **Background and Significance**

Tracheal intubation is one of the most important interventions in the stabilization of critically ill or injured children. Advanced airway skills training is one of the major pillars of the ACGME pediatric program requirements for resident and fellowship education (Accreditation Council for Graduate Medical Education, 2007). The pediatric airway presents unique anatomic challenges depending on the patient age, size and underlying condition. These challenges, coupled with low frequency of pediatric trainee exposure to advanced airway management, make tracheal intubation procedural competency difficult to achieve. As a result, tracheal intubation in infants and children is associated with high levels of operator stress as well as patient morbidity and mortality.

The ability to manage the pediatric airway, which includes anticipating potential difficulties and choosing an appropriate approach, remains one of the most vital skills to develop when caring for critically ill children. Provider training level has been found to correlate with patient outcome during advanced airway management in selected environments including the operating room, delivery room and Neonatal Intensive Care Unit (NICU). Pediatric trauma patients intubated by less experienced emergency medical personnel in the field have increased morbidity and mortality when compared to similar patients intubated by pediatric-trained hospital personnel. A limited number of studies from neonatal resuscitation demonstrated that resident trainee success rates are moderate at best, with 1/3 of upper level pediatric residents unable to intubate a very low birth weight (<1500 grams) neonate. The RRC agreed that neonatal intubation is a critical skill, but respondents to a survey sent to Residency Program Directors determined that "many residents do not develop competence in that area" and that a "more robust and standardized method is needed for teaching procedural skills and for documenting

Version #3

Date: September 19, 2017

pg. 2

competence". A survey of pediatric emergency room directors found that the number of intubations necessary to maintain skill in this area was inadequate. Even more concerning is that procedural skills such as intubation deteriorate rapidly over time (within the first year).

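### No lead outcome is named for the arm comparison, the arm models use no baseline covariate, and any lead test must allow for allocation by month and repeated intubations

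*SAP*

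**What the plan says.** The SAP's Statistical Analysis is one paragraph. For the arms: "Logistic regression will be utilized to compare overall and first-time intubation success rates between the control and intervention groups". For training level, separately: "Logistic regression will be used to compare the difference in success rate between training level groups". For counts: "a negative binomial regression will be utilized to assess difference in overall and first-time intubation success counts", without saying which groups are compared. For the survey: "Chi-square testing will be utilized for comparing end of survey comfort". Its one multiplicity statement is a "correction to account for test multiplicity will be used to analyze the difference in baseline measures and demographics".

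Aim 1 of the protocol expects "enhanced success in intubation as determined by the number of attempts and time required for intubation of live patients". Methods lists first-attempt success, total attempts, and successes inside the 30-second NRP limit. Aim 2 expects that "pediatric residents will have increased satisfaction scores and confidence for intubating live patients in the Intervention Group vs. the Control Group". No outcome in either document is called primary.

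Methods has every participant complete a baseline assessment that includes simulation, and allocates residents by their NICU month. The Abstract speaks of training in alternating months. Methods expects 80 residents to enrol; the Evaluation Plan gives 27 per group. On prognosis, Background says "Provider training level has been found to correlate with patient outcome during advanced airway management in selected environments". The SAP mentions neither month nor resident, and does not state the unit of analysis for the logistic models.

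**The concern.** Three gaps meet in the same arm comparison.

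First, with no ranked outcome and no correction, a positive result could be claimed from whichever success rate turns out significant. The correction is spent on baseline tests, where a false positive matters little.

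Second, a small trial collects two variables that may predict intubation success and uses neither in the models that answer its main question.

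Third, residents in the same month share their allocation, and one resident's intubations are likely to resemble each other. If the logistic model treats each intubation as independent, its p-value will tend to be too small. Naming a lead outcome or adding covariates does not cure that.

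**Working it through.** **The plan's own figure.** The Evaluation Plan's 27 per group comes without outcome, effect, error rate or power, so it can be neither reproduced nor refuted. For two means, n = 2(z₁₋α/₂ + z₁₋β)²/d². With two-sided 5% and 80% power, d = 0.7625 gives 2(1.960 + 0.842)²/0.581 = 27; at 90% power, d = 0.88 does. It serves below only as a planning size, beside 40 per arm (80/2, assuming equal arms).

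**Outcomes side by side.** Aim 1 uses attempts and time. Methods uses first-attempt success, total attempts and successes within 30 seconds. The SAP uses overall and first-time success. First-time success is the number of attempts cut at one, so it bears on Aim 1. Total attempts and time are not themselves modelled, and the SAP does not say whether success includes the 30-second limit.

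**Multiplicity.** Assume each test is two-sided at 5%, since the documents give no level. Two independent tests: 1 − 0.95² = 9.75%. Perfectly dependent tests: 5%. Overall success contains first-time success, so the truth lies between. One simulation of valid tests gave about 6-8%. Another, of month-level adjusted tests, gave 7.4-10.1%; its upper end exceeds 9.75% because the component tests themselves ran at 4.6-5.9%. Hence roughly 6-10%. If the count models also compare arms there are four tests; independence would give 1 − 0.95⁴ = 18.5%, an upper guide only, because they reuse the same events.

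**Covariates.** Every input is assumed: independent residents with one outcome each, three training levels and a standard normal score, log-odds slopes 0.2 (weak), 0.6 (moderate) or 1.0 (strong), success 45% vs 75%, 10,000 null and 10,000 alternative trials. Size-matched power (cut-off at the null 95th percentile), unadjusted to adjusted:

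| Per arm | Weak | Moderate | Strong |
|---|---|---|---|
| 40 | 79.7 to 79.2% | 79.5 to 83.7% | 79.0 to 87.3% |
| 27 | 65.3 to 62.8% | 65.2 to 66.5% | 64.4 to 72.6% |

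A separate run at 27 per arm with moderate covariates gave about 66 to 69%. The moderate gain is therefore about 4 points at 40 and 1-3 at 27; the weak case loses 65.3 − 62.8 = 2.5 points at 27.

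At 27 per arm the adjusted likelihood-ratio test had type I error 5.8-6.1% in this simulation and 6.5-6.9% in another of 2,000 runs (Monte Carlo standard error √(0.05 × 0.95/2000) = 0.5 points), so about 5-8% overall. The adjusted Wald test ran at 4.6-5.2%.

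**Month and resident.** Assumed: 20 or 14 months of 4 residents in alternating arms, a mean of 1.5 or 3 intubations each, month/resident ICC of 0/0, 0.05/0.10 or 0.10/0.20, and 4,000 trials per scenario. An unadjusted intubation-level logistic test had type I error 5.9-19.1%.

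A rough hand check uses design effect D = 1 + (m − 1)ρ_month + (k − 1)(ρ_resident − ρ_month), with m intubations per month and k per resident. Here ρ_resident is read as the total correlation between one resident's intubations, and the error rate is P(|Z| > 1.96/√D).
- m = 4 × 1.5 = 6, ICC 0.05/0.10: D = 1 + 0.25 + 0.025 = 1.275, error rate 8.3%.
- m = 4 × 3 = 12, ICC 0.10/0.20: D = 1 + 1.10 + 0.20 = 2.30, error rate 19.6%.

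The month-level two-stage t test held 4.4-5.7% unadjusted and 4.6-5.9% adjusted. With 45% vs 70%, ICC 0.05/0.10 and moderate covariates, adjustment moved its power from 65.3 to 69.5% (20 months, mean 1.5), 80.6 to 87.5% (20, mean 3), 48.6 to 52.0% (14, mean 1.5) and 64.7 to 72.4% (14, mean 3).

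**Comfort (conditional).** Assumed proportional-odds shift with odds ratio 2.5, clustering ignored, chi-square vs rank test. At 40 per arm: five levels 37.1 vs 62.0%, three levels 42.5 vs 52.4%, yes/no 53.5 vs 53.5%. At 27 per arm: 24.3 vs 45.2%, 29.4 vs 37.3%, 35.6 vs 35.5%.

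**The case against.** Adjustment is a preference. An unadjusted logistic regression is a legitimate analysis, and a reader might wrongly infer that leaving out the covariates biases the comparison. It does not. Nor is the precision free: at the planned size, weak covariates cost power and the adjusted likelihood-ratio test is slightly liberal. The documents do not show that the covariates are prognostic. Background ties training level to patient outcome in certain settings, not to success by residency year within one program, and the Abstract calls it unknown whether manikin skill carries over to live patients. All of this stands, and the strong-covariate column has no support in the documents.

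A reader might also infer that the SAP analyses nothing Aim 1 asks about. That goes too far, because first-time success is a form of the attempts outcome.

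The 6-19% describes one implementation. The SAP does not state its unit of analysis, so that is a risk left open, not a documented error. The SAP's allowance for over-dispersion is stated only for the count models, and no month term is named there.

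Finally, a reader might infer that chi-square wastes power for comfort. The scale is not given, a yes/no item loses nothing, and the simulated shifts favour the ordered test.

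**Conclusion.** The point holds in three parts, in this order of weight.

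1. No outcome is ranked and the arm tests are uncorrected. This rests on the text alone. Its size, roughly 6-10% instead of 5% for the two rate tests, assumes that each test is valid at 5%.
2. The plan does not say how the arm tests handle allocation by month or repeated intubations. Ignoring both gives about 6-19% type I error for month ICCs of 0 to 0.10 and resident ICCs of 0 to 0.20, all assumed. Any lead test has to meet this condition.
3. Available covariates go unused. This is a missed opportunity, not an invalid analysis; the gain is modest, depends on unknown prognostic strength and can be negative at 27 per arm.

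The comfort point is secondary and conditional on the scale. Confidence is medium: the textual gaps are clear, but every effect size and correlation is an assumption.

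**What to change.** - Have the sponsor reconcile Aim 1 with the SAP and name one lead outcome and one model, tested at 5%. First-time success is a candidate already in the SAP. State whether success includes the 30-second limit.
- Test the other Aim 1 arm comparisons by Holm only if the lead test succeeds, including the count models if they compare arms.
- Adjust the lead model for training level and the pre-training simulation result only, and define both scales.
- Make the test and the interval for the reported effect both allow for month and repeated intubations. One option is a month-level two-stage analysis: fit the covariate-only model, average residuals by month, compare arms by a t test on months minus 2 degrees of freedom, and report its risk difference with the matching interval.
- Do not use the adjusted likelihood-ratio test at 27 per arm without a small-sample check.
- State the comfort scale. With three or more ordered levels, use an ordered test that also allows for month. With a yes/no item an ordered test gains nothing, though allocation by month still applies.

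Cost: SAP wording and minor programming on data already planned. Weak covariates bring no gain or a small power loss, and later p-values are slightly larger under Holm. A lead outcome of attempts or time would need a new analysis.
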